7.1 Adverse Events

An adverse event (AE) is defined as an undesirable physical, psychological, or behavioral effect experienced by a subject related to headaches in conjunction with his/her participation in the clinical study, whether or not device related. Any subject may experience adverse events or complications while enrolled in the study. Should they occur, these events will be reported to the sponsor as detailed in section 7.3.1.

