After completion of study activities, subjects will return the glasses specific to their study arm, and be asked to complete a study questionnaire, to provide feedback regarding the wearability and ease of use of the glasses. Subjects will also be asked to provide an opinion as to which type of device they believe they were assigned to (Avulux[®] vs. control/sham vs. do not know).

7. Safety Reporting

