7.2 Serious Adverse Events

A *serious adverse event* (SAE), as defined by the International Conference on Harmonization (ICH) guidelines, is any adverse event that results in any of the following outcomes:

1. Death;

2. Life-threatening outcome (*i.e.* immediate risk of death from the reaction as it occurred);
3. Inpatient hospitalization or prolongation of existing hospitalization;
4. Persistent or significant disability or incapacity; or
5. Congenital anomaly.

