7.3 Reporting of Events

7.3.1 Adverse Events

Adverse events will be reported to the sponsor in a timely manner. A case report form shall be completed for each event, with description of the event, onset date, end date, relation to study device, any treatment rendered and the outcome.

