7.3.2 Serious Adverse Events

Serious adverse events should be reported to the sponsor within 24 hours of awareness of the event. The investigator or designee should report the event via telephone, email or fax with details describing the event, onset date, end date, severity of event, relation to study device treatment and outcome. If all details are not known at the time of reporting, an initial report is filed followed by a detailed report within 7 working days. It is the responsibility of the investigator to inform the IRB/EC as applicable according to their IRB/EC policies. It is the responsibility of the sponsor to inform the other sites of the event.

8. Risk/Benefit Analysis

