8.1 Risks

There are no anticipated risks to study subjects as a result of application of the device. Any potential discomfort experienced from use of the device would be mitigated by removal of the device.

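### Section 7.1 counts only headache-related effects as adverse events, and the serious-event rule and the safety tables inherit that limit

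*Combined protocol and SAP*

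**What the plan says.** Section 7.1 defines an adverse event as "an undesirable physical, psychological, or behavioral effect experienced by a subject related to headaches in conjunction with his/her participation in the clinical study". It adds that the event counts whether or not it is device related. The same section then says "Any subject may experience adverse events or complications while enrolled in the study" and refers to section 7.3.1 for reporting. The term *complications* is not defined.

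The later sections use the defined terms:

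- Section 7.2: a serious adverse event "is any adverse event that results in any of the following outcomes", followed by five outcomes.
- Section 7.3.1: "Adverse events will be reported to the sponsor in a timely manner", with a case report form for each event.
- Section 7.3.2: "Serious adverse events should be reported to the sponsor within 24 hours of awareness of the event".
- Section 11.2.9: adverse events are counted for each device, their severity and relationship to study procedures are summarised, and serious adverse events are listed one by one.

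Section 8.1 states "There are no anticipated risks to study subjects as a result of application of the device", and continues: "Any potential discomfort experienced from use of the device would be mitigated by removal of the device".

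**The concern.** The definition restricts the kind of effect that counts. The clause on device causality leaves that restriction in place: it says that the cause of a headache-related effect does not matter, not that an effect unrelated to headache qualifies. A safety definition for a wearable device should at least admit harm from wearing it. Here, harm with no headache link is screened out before anyone is asked about its relation to the device.

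Two things are at stake. The first is subject protection: a site that follows 7.1 literally has no 24-hour duty to tell the sponsor about a serious injury unconnected with headache. The second is the evidence for the statement in 8.1 that no risks are anticipated. The analysis in 11.2.9 is the only planned safety analysis that could test that statement, and its data need not contain the events that would contradict it.

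**Working it through.** The plan gives no figure on this point, so there is none to reproduce. The check has two parts.

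**Tracing the definition**

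1. Section 7.1: adverse event = undesirable effect AND headache-related AND in conjunction with participation. Device causality is left open.
2. Section 7.2: serious adverse event = adverse event AND one of five outcomes. It must therefore meet all the conditions in step 1.
3. Section 7.3.1 covers adverse events, and section 7.3.2 (24 hours) covers serious adverse events. Neither names a wider class.
4. Section 9: at discontinuation, the investigator notes the reason and any potential adverse events. The same term applies.
5. Section 11.2.9 counts adverse events and lists serious ones. Again there is no wider class.
6. No section restates the definition without the headache condition.

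Take a fall while wearing the glasses that leads to hospitalization and has no headache link. It fails step 1, so it fails step 2, and steps 3 and 5 do not reach it. The same holds for discomfort from the glasses that is not related to headache, although 8.1 foresees discomfort. The fall is an illustration only; the document does not name it as a device risk.

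The other contacts with subjects do not close the gap. The weekly contacts in section 6.4 are described as checks on device wear, headache recording and barriers to adherence. The questionnaire after study activities asks subjects "to provide feedback regarding the wearability and ease of use of the glasses". It may pick up discomfort, but it is not adverse event reporting.

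**What an empty table would mean**

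Inputs from section 11.1: at least 34 subjects enrolled per arm, and 27 per arm after the planned dropout of up to 20% (34 × 0.80 = 27.2).

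If every event is reportable and none occurs among n device users, the one-sided 95% upper bound on the per-subject risk is 1 − 0.05^(1/n):

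| Device users per arm | Calculation | Upper bound |
|---|---|---|
| 34 | 1 − 0.05^(1/34) = 0.0843 | 8.4% |
| 27 | 1 − 0.05^(1/27) = 0.1050 | 10.5% |

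This assumes that all 34 enrolled, or all 27 completing, subjects used the device, because 11.2.9 analyses device users only. Under the wording of 7.1 the formula does not apply to non-headache events: a zero may mean that none occurred or that none had to be recorded.

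**The case against.** The strongest reply is that the document shows a wider intent in several places.

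- **Complications.** Section 7.1 mentions complications beside adverse events and appears to send both to 7.3.1, and that sentence carries no headache condition. This stands in part: routine reporting under 7.3.1 is ambiguous rather than clearly closed. But the term is undefined, 7.3.1 itself speaks only of adverse events, and the term does not appear in 7.2, 7.3.2 or 11.2.9. It cannot bring an event under the 24-hour rule or into the tables.
- **External standards.** Section 7.2 attributes the serious event definition to ICH, one of its outcomes is a congenital anomaly, and section 10 commits the study to GCP and IDE regulations. These suggest that the limit is a drafting slip, and some sites may report more widely. The operative words of 7.2 still rest on the term that 7.1 defines. If sites follow different texts, capture will differ across the three or more sites.
- **Timing.** Subjects put the glasses on at aura or migraine onset, so many device effects would arise during an attack and might be called headache-related. That is fair, and the gap is limited to events with no headache link. Timing alone does not establish such a link.
- **Withdrawals.** Section 9 records why a subject discontinues, so discomfort that leads to withdrawal would leave a trace. That trace is neither an adverse event report nor part of 11.2.9.
- **The bounds.** They are generic zero-event limits and do not measure how many events would be missed. This is correct. The case of 27 also drops subjects whom 11.2.9 would keep if they had worn the device. The conclusion does not depend on either figure.

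**Conclusion.** The concern holds. As written, an undesirable effect or serious injury with no headache link is neither an adverse event nor a serious adverse event, is not subject to the 24-hour rule, and need not appear in the safety tables. This is a stated rule that gives the wrong result, not a missing detail.

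The number of events affected cannot be estimated, because the document gives no event rates and does not show how sites would apply 7.1. The loss is that a blank entry for non-headache events would support no statement about risk, where full capture would support an upper bound of about 8% to 11% per arm. No efficacy objective is affected. The point should be corrected because it concerns subject protection, and events never recorded may not be recoverable at analysis.

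**What to change.** In section 7.1, delete the words *related to headaches*. An adverse event is then any undesirable effect of the kinds already listed that occurs during participation, whatever its cause. In the same section, define *complications* or delete the term, so that 7.1, 7.2, 7.3 and 11.2.9 share one scope. Sections 7.2, 7.3 and 11.2.9 then need no change for the wider definition to reach them.

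Two optional additions would strengthen capture: a question about any undesirable effect at the weekly contact in section 6.4, and a separate summary of ocular events and falls in section 11.2.9. The correction does not depend on them.

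The cost is the deletion of one phrase, the definition or deletion of one word, and a few more adverse event forms.

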7.2 Serious Adverse Events

A *serious adverse event* (SAE), as defined by the International Conference on Harmonization (ICH) guidelines, is any adverse event that results in any of the following outcomes:

1. Death;

2. Life-threatening outcome (*i.e.* immediate risk of death from the reaction as it occurred);
3. Inpatient hospitalization or prolongation of existing hospitalization;
4. Persistent or significant disability or incapacity; or
5. Congenital anomaly.

7.3 Reporting of Events

7.3.1 Adverse Events

Adverse events will be reported to the sponsor in a timely manner. A case report form shall be completed for each event, with description of the event, onset date, end date, relation to study device, any treatment rendered and the outcome.

7.3.2 Serious Adverse Events

Serious adverse events should be reported to the sponsor within 24 hours of awareness of the event. The investigator or designee should report the event via telephone, email or fax with details describing the event, onset date, end date, severity of event, relation to study device treatment and outcome. If all details are not known at the time of reporting, an initial report is filed followed by a detailed report within 7 working days. It is the responsibility of the investigator to inform the IRB/EC as applicable according to their IRB/EC policies. It is the responsibility of the sponsor to inform the other sites of the event.

8. Risk/Benefit Analysis

8.1 Risks

There are no anticipated risks to study subjects as a result of application of the device. Any potential discomfort experienced from use of the device would be mitigated by removal of the device.

8.2 Benefits

The anticipated benefit of the device is the reduction in headache severity in patients with migraine headaches. Information gained from this study may aid in the future management of patients with episodic migraine headaches.

9. Subject Withdrawal

In accordance with Good Clinical Practice (GCP) guidelines, subjects who have consented to participate in the study are free to withdraw consent and discontinue participation in the study at any time, and without prejudice to further treatment as required for their condition.

If a subject decides to discontinue participation in the study, the investigator will note the reason for the discontinuation (and any potential AEs) on the applicable case report form.

10. Administrative Considerations

This protocol was designed and will be conducted, recorded, and reported in compliance with Good Clinical Practice (GCP) guidelines and with applicable U.S. Food and Drug Administration (FDA) Investigational Device Exemption (IDE) regulations.

10.1 Prior to Study Initiation

The following will be provided to the sponsor from the study site, prior to study initiation:

- Curriculum Vitae of the investigator;
- The “Statement of Compliance” page of the protocol, signed and dated by the investigator;
- An independent IRB/EC membership list current at the time of the review of this protocol;
- Financial Disclosure Form, signed and dated by the investigator;
- Written verification of IRB/EC approval for the study; and
- A duly executed clinical study agreement.

10.2 Amendments

Amendments to this study protocol must be agreed upon in writing between the investigator and the sponsor. Written verification of IRB/EC approval will be obtained before any amendment is implemented which affects subject safety or materially alters the study design. Modifications of the protocol which are administrative in nature do not require IRB/EC approval, but will be submitted to the IRB/EC for informational purposes.

If there are changes to the informed consent form utilized by a site, written verification of IRB/EC approval of the new form must be forwarded to the sponsor, along with a copy of the new form. If the changes in the content of the consent form are directly related to information that may influence the subject’s decision to participate in the study, the subject may need to be reconsented.

10.3 Financial Disclosure of Clinical Investigators

The clinical investigator(s) participating in this study shall complete a financial disclosure form, so as to provide sufficient and accurate financial information to the sponsor pertaining to:

- Any arrangements between the sponsor and clinical investigator whereby the value of compensation to the investigator for conducting the study could be influenced by the outcome of the study;
- Any significant payments or other forms of compensation from the sponsor, such as grants to fund ongoing research, compensation in the form of equipment, retainers for ongoing consultation, or honoraria;

- Any proprietary interest in the product to be developed and held by the investigator involved in the study; and
- Any significant equity interest in the sponsor held by the investigator, his/her spouse or dependent children.

10.4 Subject Informed Consent

This study will be conducted in compliance with the principles of 'Informed Consent' described in the Declaration of Helsinki and FDA 21 CFR Part 50. It is the responsibility of the investigator, or designee, to obtain written informed consent from each subject prior to the subject's inclusion in the study.

The sponsor will provide each investigator with a sample informed consent document that the site may modify to meet individual IRB/EC requirements. The investigator should provide the sponsor with a copy of the proposed consent form, preferably prior to submitting it to the IRB/EC, so that the sponsor may ensure that all appropriate and required elements are incorporated into the document.

Prior to study initiation, the investigator must provide the sponsor with a copy of the informed consent form approved by the IRB/EC, and a copy of the IRB/EC letter stating that formal approval has been granted by the institution.

Study subjects must provide written consent using the IRB/EC-approved informed consent form in effect at the time of presentation of the subject to the study site. Participating subjects in the State of California will also be provided with the *Experimental Subject's Bill of Rights* as part of the informed consent form.

A copy of the IRB/EC-approved informed consent form and a copy of each subject's signed consent form will be maintained by each investigator in the site's study file. A copy of the signed and dated informed consent form must be given to each study subject. The original informed consent form for each subject must be kept on file at each of the participating study sites for a minimum retaining period, in accordance with applicable regulatory authority recommendations (refer to section 10.10).

10.5 Subject Confidentiality

The sponsor and the study investigators shall make every effort to protect the confidentiality of subjects participating in the study. All study information and data with respect to individual study subjects will be considered confidential. Only authorized personnel will have access to this confidential information.

Subject specimens will be identified using a unique identifier. All data used in the analysis and reporting of this evaluation will be without identifiable reference to the subjects.

10.6 Study Registration

Study information and final study results will be entered in the ClinicalTrials.gov registry database in compliance with the FDA Modernization Act of 1997 and the FDA Amendments Act of 2007.

10.7 Source Documents

The subject's site visit must be fully documented on source document worksheets or in the subject's medical records, or a combination of both.

During the monitoring process, information entered into the study case report forms will be verified against the source worksheets or subject medical records.

10.8 Device Accountability

Only the investigator and study staff identified in the clinical research agreement and/or study logs on file with the sponsor and at the study site may have access to the investigational device. The investigator must maintain a full accountability for any devices received. An accountability log will be provided to maintain current and accurate inventory records covering the receipt and return of the devices.

At the conclusion of the study, the site will return the devices to the sponsor. The site shall retain a copy of the accountability log for its study files.

10.9 Device Labeling

The study glasses and sham glasses will be labeled in accordance with U.S. federal regulations applicable to an investigational device. All device labeling, operating instructions, device warnings or precautions, and informational materials will include the following statement:

CAUTION - THIS IS AN INVESTIGATIONAL DEVICE. LIMITED BY FEDERAL (OR U.S.) LAW TO INVESTIGATIONAL USE.

--

10.10 Study Monitoring

Clinical site monitoring is conducted to ensure that the rights and well-being of human subjects are protected, that the reported study data are accurate, complete, and verifiable, and that the conduct of the trial is compliant with federal regulations, agreements with the sponsor, the currently approved protocol, and with any requirements imposed by the IRB/EC.

Site monitoring will be performed by a third-party contract research organization (CRO) working on behalf of the sponsor. A Clinical Monitoring Plan (CMP) will be developed to establish the plan for study oversight.

On-site monitoring is anticipated throughout the course of the study. The sponsor will be provided with written reports of these visits, and the sites will be provided with a follow-up letter describing the findings and defining any outstanding issues or action items required.

10.11 Retention of Study Records

The investigator will maintain adequate records for the study including informed consent forms, source documents (as applicable), medical records, safety reports (as applicable), and other pertinent study data.

For participating U.S. study sites, all records for this study must be retained by the Investigator for a minimum period of:

- two (2) years after the FDA approves the marketing notification for the product, **or**
- two (2) years following termination of the study if no marketing notification is ever sought or approved,

whichever is the longer elapsed time.

To avoid any possible misunderstandings, the investigator will contact the sponsor prior to the planned destruction of any study records, or if the investigator leaves the institution where the study was conducted. The investigator will notify the sponsor in the event of accidental loss or destruction of any study records.

10.12 Protocol Termination

Both the sponsor and the investigator have the right to terminate the study at their discretion, with written notice to the other party. This action should be taken only after appropriate consultation between the sponsor and investigator or institution. Termination of the study shall not affect the rights and obligations of either of the parties prior to the date of termination.

11. Data Analysis

11.1 Sample Size Justification

A pilot evaluation of the Avulux® and control/sham devices (n = 10 subjects using each type of device) demonstrated that users of the Avulux® device reported a mean decrease of 4.1 points in pain score (standard deviation = 1.9 points) after an elapsed time of 2 hours, and users of the placebo device reported a mean decrease of 1.9 points in pain score (standard deviation = 1.5 points) after an elapsed time of 2 hours. The difference between the performance of the two devices was statistically significant ($p = 0.004$).

Assuming that subjects with severe or very severe migraine headaches achieve a mean 4-point improvement in pain score when using the investigative device and at most a mean 2-point improvement when using the control/sham device, and assuming a standard deviation of at

most 2.0 points when estimating the mean difference in pain scores in individual study subjects after application of either device, a sample size of 27 subjects per study arm provides a minimum statistical power of 95% to detect a significant difference in mean results for the primary endpoint variable between the two (2) device types, at a significance level of $\alpha = 0.05$. Given an estimated dropout rate of up to 20% in each study arm, a minimum of 34 subjects per arm (or 68 total subjects) are required to be enrolled in this study.

The above assumptions imply that the mean improvement in pain score after 2 hours will be at least 2 points higher for the Avulux® device than for the control/sham device. Meta-analyses have shown that the minimal clinically important difference (MCID) to detect changes in acute pain as measured on the 11-point pain scale is 1.7 points;^{2,3} therefore, a 2-point difference in mean improvement between study devices is considered to be clinically meaningful.

11.2 Proposed Analyses

A statistical analysis plan, containing detailed information regarding the proposed statistical analyses of study data, will be created and approved prior to database lock.

Unless otherwise stated, all statistical testing will be two-sided and will be performed using a significance level of $\alpha = 0.05$.

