3.1 Primary Objective

The primary objective of this study is to evaluate the efficacy of the Avulux® device in reducing the impact of migraine headaches, as measured by improvement in an 11-point pain scale after 2 hours of device application, when compared to a control/sham device.

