3.2 Secondary Objective

The secondary objective of this study is to evaluate the efficacy of the Avulux® device in reducing the impact of migraine headaches, as measured by improvement in an 11-point pain scale after 4 hours of device application, when compared to a control/sham device.

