4.2 Secondary Endpoint

The secondary endpoint variable is the change in migraine pain as measured on an eleven-point pain scale, defined as the pain score after an elapsed time of 4 hours following application of the device minus the pain score at onset of migraine symptoms, with respect to the first severe or very severe migraine headache (defined as a pain score of 6 or greater at onset of migraine symptoms) experienced by an enrolled subject.

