11.2.1 Analysis Populations

The *intention-to-treat* (ITT) population shall be defined as the population of all enrolled subjects who were assigned to a study group and who experienced a minimum of one severe or very severe headache within 4 weeks of enrollment. This population shall include subjects who were non-compliant with study procedures, and subjects who were assigned to the incorrect device specific to their study group.

The *per-protocol* population shall be defined as the population of all enrolled subjects who were assigned to the correct device specific to their study group, who experienced a minimum of one severe or very severe headache within 4 weeks of enrollment, and who were compliant with study procedures throughout the duration of their enrollment in the study.

Analyses of the primary and secondary endpoints shall be conducted using data from intention-to-treat population. Analyses of exploratory endpoints shall be conducted using data from the per-protocol population.

² Olsen MF, Bjerre E, Hansen MD *et al.* Pain relief that matters to patients: systematic review of empirical studies assessing the minimum clinically important difference in acute pain. *BMC Medicine* 2017, 15: 35.

³ Farrar JT, Young JP Jr., LaMoreaux L *et al.* Clinical importance of changes in chronic pain intensity measured on an 11-point numerical pain rating scale. *Pain* 2001, 94: 149-158.

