11.2.5 Analysis of Primary Endpoint

The null hypothesis to be tested is

$$H_0: D_A - D_{C/S} = 0,$$

where D_A is the change in pain score after an elapsed time of 2 hours using the active device, and $D_{C/S}$ is the change in pain score after an elapsed time of 2 hours using the control/sham device.

⁴ Van Buuren S and Goothius-Oudshoorn K. *mice*: Multivariate imputation by chained equations. *Journal of Statistical Science* 2011, 45: 1-67.

In order to assess whether there is a possible baseline effect, the mean baseline pain score (*i.e.* mean pain score at symptom onset) using the active device shall be statistically compared to the mean baseline pain score using the active/sham device, using a two-sample *t*-test at a significance level of $\alpha = 0.05$.

In order to assess whether there is a possible effect of rescue medications on the primary endpoint, the proportion of subjects using rescue medications within 2 hours of symptom onset will be statistically compared between the two study arms, using Fisher's exact test at a significance level of $\alpha = 0.05$.

If there is no significant difference in baseline pain scores and no significant difference in early use of rescue medications between the two device types, the null hypothesis will be tested using the difference between the change in pain scores after 2 hours using the active device and the change in pain scores after 2 hours using the control/sham device.

The distributions of these differences will be tested for normality using the Shapiro-Wilk test at a significance level of $\alpha = 0.05$. If the distributions are consistent with a hypothesis of normality, the above null hypothesis will be tested using a two-sample *t*-test; otherwise, the null hypothesis will be tested using a non-parametric Mann-Whitney test. The mean and associated 95% confidence interval for the true difference between the two devices will be computed, along with the *p*-value associated with the null hypothesis.

If there is a significant difference in baseline pain scores and/or early use of rescue medications between the two study arms, an analysis of covariance (ANCOVA) model shall be fitted to the data, relating the difference in pain scores after 2 hours to the device type (active vs. control/sham), while controlling for any significant covariates. A *p*-value associated with the test of the hypothesis of no effect of the active device on change in pain score after 2 hours will be computed.

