11.2.6 Analysis of Secondary Endpoint

In order to compare the mean change in pain score after an elapsed time of 4 hours using the active device to the mean change in pain score after an elapsed time of 4 hours using the control/sham device, the analyses as described in section 10.2.5 for the primary endpoint shall be followed.

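### The 4-hour secondary endpoint is tested at the full two-sided 0.05 with no testing order, so it can be formally significant even if the 2-hour primary fails; one sentence in section 11.2.6 would settle this.

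*Combined protocol and SAP*

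**What the plan says.** The protocol has one primary and one secondary efficacy objective, worded alike apart from the time point. Section 3.1 judges the device "as measured by improvement in an 11-point pain scale after 2 hours of device application, when compared to a control/sham device"; section 3.2 judges it "as measured by improvement in an 11-point pain scale after 4 hours of device application, when compared to a control/sham device".

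Both endpoints concern the same headache and subtract the same onset score. Section 4.2 defines the 4-hour score "minus the pain score at onset of migraine symptoms, with respect to the first severe or very severe migraine headache", and section 4.1 does the same for the 2-hour score.

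The two tests share a population (section 11.2.1): "Analyses of the primary and secondary endpoints shall be conducted using data from intention-to-treat population". They also share a procedure. In section 11.2.5, if neither baseline pain nor early rescue use differs between arms and normality is not rejected, "the above null hypothesis will be tested using a two-sample *t*-test; otherwise, the null hypothesis will be tested using a non-parametric Mann-Whitney test"; if baseline pain or early rescue use does differ, an ANCOVA is fitted. For the 4-hour endpoint, section 11.2.6 says only that "the analyses as described in section 10.2.5 for the primary endpoint shall be followed". The primary analysis is in fact in section 11.2.5, and that is evidently what is meant.

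The level comes from section 11.2: unless otherwise stated, "all statistical testing will be two-sided and will be performed using a significance level of" 0.05. Nothing states otherwise for the secondary endpoint. No section gives a testing order, a gate, a split of alpha or any other multiplicity rule.

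**The concern.** Calling one endpoint primary and the other secondary ranks them, but it does not say how to read a significant 4-hour result when the 2-hour result is not significant. As written, that outcome meets the plan's own criterion for significance on a stated efficacy objective. The trial then has two routes to a formally significant efficacy result, and the chance of taking at least one of them by luck exceeds that of a single test.

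What is at stake is the standing of a 4-hour finding after a failed primary. If the rule is left until the data are known, the choice between confirmatory and descriptive could look driven by the result.

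**Working it through.** **1. The plan's own figure.** Section 11.1 assumes a difference of 4 − 2 = 2 points, SD 2.0, two-sided 0.05 and 95% power, for the primary endpoint only.

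- Normal approximation: n per arm = 2 × (1.960 + 1.645)² × 2.0² / 2² = 26.0, so 26.
- Exact t-test power is 94.2% at 26 per arm and 95.0% at 27, which reproduces the stated 27.
- Dropout of 20%: 27 / 0.80 = 33.75, so 34 per arm and 68 in total, as stated.

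The sample size therefore rests on the 2-hour test at the full 0.05. The documents state no joint error rate for the two endpoints, so there is none to reproduce.

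**2. Joint error without an order.** Let Z1 and Z2 be the 2-hour and 4-hour test statistics, with correlation ρ and no effect at either time.

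- Either direction: 1 − P(|Z1| < 1.96 and |Z2| < 1.96).
- Favouring the device only: 1 − P(Z1 < 1.96 and Z2 < 1.96), with positive values favouring the device.
- Only the 4-hour test significant, either direction: the first quantity minus 5%.

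The documents do not give ρ, so it is an assumption. A substantial positive value is plausible because both changes come from the same headache and share an onset score. As a check, two t-tests with 27 per arm were simulated, with 100,000 trials for each ρ.

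| ρ (assumed) | At least one, either direction | Same, simulated | At least one favouring device | Only 4 h, either direction |
|---|---|---|---|---|
| 0 | 9.75% | – | 4.9% | 4.75% |
| 0.5 | 9.1% | 9.1% | 4.5% | 4.1% |
| 0.7 | 8.3% | 8.2% | 4.2% | 3.3% |
| 0.8 | 7.8% | 7.8% | 3.9% | 2.8% |
| 0.9 | 7.0% | 7.0% | 3.5% | 2.0% |
| 1 | 5.0% | – | 2.5% | 0% |

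**3. Joint error with a fixed order** (4 hours tested only if 2 hours is significant).

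- No effect at either time: at least one false significance requires the 2-hour test to reject, so the rate is 5.0% in either direction and 2.5% favouring the device. A 2-hour result favouring sham followed by a 4-hour result favouring the device adds at most 0.025 × 0.025 = 0.06% (at ρ = 0), and less for positive ρ.
- True 2-hour effect as planned, no 4-hour effect: a false 4-hour result occurs at most 5% of the time with or without the order. Simulated at ρ = 0.7 and 27 per arm, it is 5.0% without and 3.9% with.

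The order therefore matters when neither time point has an effect, and what it removes is the last column of the table.

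**The case against.** The strongest reply is that the endpoints are already ranked. There is one primary endpoint, it alone drives the sample size, and no section says that the trial succeeds on the 4-hour result alone. On that view a secondary p-value after a failed primary is supportive at best. This stands in part: the joint rate matters only if such a result is treated as confirmatory, which the plan neither allows nor rules out. A label is not a testing rule, however, so the gap remains.

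Section 11.2 also promises a separate, detailed statistical analysis plan before database lock. An order could be set there. That shows the omission may not be final; it does not supply the rule.

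Three stronger readings are tempting and are not supported:

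- A reader might infer that the plan's 0.05 is breached. It is not. Section 11.2 sets a level for each test, the primary keeps its nominal 5%, and no familywise rate is promised.
- A reader might take 7% to 9% as the chance of a false claim that the device works. Those rates include results favouring sham; for claims favouring the device the figures are about 3.5% to 4.5% against 2.5%. The relative excess is essentially the same. The range also rests on an assumed correlation.
- A reader might infer that the 4-hour result is unsound because rescue medication has longer to act on it. Cumulative use by 4 hours cannot be lower than by 2 hours. But section 6.4 asks subjects to avoid abortive medication for the first four hours of an attack and to document any use, and the documents give no usage figures. The point does not rely on this.

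The exploratory endpoints in section 11.2.7 are tested at the same level. Leaving them outside the family is a choice, and a reasonable one given their label.

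**Conclusion.** The concern holds in a limited form. The plan lets the 4-hour endpoint be declared significant at two-sided 0.05 whatever the 2-hour result. With no effect at either time, at least one of the two tests is significant in either direction 7.0% to 9.1% of the time for ρ from 0.9 to 0.5, against 5.0% with a fixed order.

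These figures assume no effect at either time, an unstated correlation and tests that each hold exactly 0.05. The preliminary tests in section 11.2.5 could shift that level; their effect was not computed. The validity of the primary conclusion is not in question. This is a cheap improvement of minor severity.

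**What to change.** Add to section 11.2.6, and carry into the separate statistical analysis plan: the 4-hour endpoint is formally tested at two-sided 0.05 only if the 2-hour primary endpoint is significant at two-sided 0.05; otherwise the 4-hour difference between arms and its 95% confidence interval are reported as descriptive. Exploratory endpoints can stay unadjusted. The cross-reference in the same section should be corrected to 11.2.5 at the same time.

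The cost is one sentence. The primary keeps its full 0.05, so 27 evaluable and 34 enrolled subjects per arm are unchanged. The downside is real but narrow: if the device works at 4 hours and the 2-hour test fails, no formal 4-hour claim can be made, although the estimate and interval are still reported. The rule should be fixed before the data are unblinded.
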